1. PROTOCOL SUMMARY

1.1 SYNOPSIS

PROTOCOL TITLE: A PHASE IIIb, OPEN-LABEL, SINGLE-ARM STUDY IN PATIENTS WITH NEOVASCULAR AGE-RELATED MACULAR DEGENERATION OR DIABETIC MACULAR EDEMA TO EVALUATE THE SAFETY OF THE 6-MG FARICIMAB PREFILLED SYRINGE

STUDY RATIONALE

The purpose of the clinical in-use study is to collect observations on the use of the 6-mg faricimab prefiled syringe (PFS) configuration to administer an intravitreal (IVT) injection to patients with either diabetic macular edema (DME) or neovascular age-related macular degeneration (nAMD) in an actual clinical use environment. Observations will be collected during the preparation and administration of a 6-mg faricimab IVT injection using the PFS configuration in accordance with the Instructions for Use (IFU) in the intended use environment. The PFS configuration consists of the faricimab 6-mg PFS together with the co-packed injection filter needle (IFN).

OBJECTIVES AND ENDPOINTS

The primary objective of this study is to collect observations on healthcare providers (HCPs) using a PFS configuration in an actual clinical use environment to prepare and administer a 6-mg faricimab intravitreal injection to patients with either DME or nAMD and as instructed in the IFU.

No patient-related efficacy or safety endpoints are planned for this study. However, in accordance with Good Clinical Practices (GCPs), adverse events (AEs), adverse events of special interest (AESIs), and serious adverse events (SAEs) occurring during the 7-day study reporting period will be summarized.

OVERALL DESIGN

The 6-mg faricimab PFS clinical in-use study is a Phase IIIb, single-arm, open-label multicenter study in patients with nAMD or DME designed to assess the ability of the intended users, HCPs, to follow the IFU to perform an IVT injection using the 6-mg faricimab PFS configuration per the intended use. The study will collect observations related to the use of the PFS configuration.

The study will be conducted in ophthalmology clinical settings. The focus of the usability observation will be on the HCP teams. The HCP team will consist of a retina specialist and any assistants who participate in any stage of the PFS preparation and administration procedure. Approximately three HCP teams will participate in this study to administer a single IVT injection of 6-mg faricimab PFS (120 mg/mL drug concentration) using the PFS configuration for a total of approximately 35 participants.

All patients will be required to have a current diagnosis of nAMD or DME with at least one eye eligible for 6-mg faricimab IVT injection, at the discretion of the retina specialist. Both previously treated and treatment-naive patients will be eligible for enrollment. Only one eye will be selected as the study eye. If both eyes are eligible, the investigator will determine which eye will be selected for study treatment (study eye).

The same retina specialist may act as the Principal Investigator and the HCP using the PFS configuration to administer faricimab. Alternatively, a sub-investigator may perform the duties of the HCP.

DISCLOSURE STATEMENT

This is a single-group device feasibility study that is not masked.

NUMBER OF PARTICIPANTS

Approximately 35 evaluable patients with nAMD or DME will be enrolled in this study.

6-mg Faricimab Prefilled Syringe—F. Hoffmann-La Roche Ltd 7/Protocol GR43742, Version 1 Note: "Enrolled" means a participant's or their legally acceptable representative's agreement to participate in a clinical study following completion of the informed consent process. Potential participants who are screened for the purpose of determining eligibility for the study but do not participate in the study, are not considered enrolled, unless otherwise specified by the protocol.

STUDY TREATMENT

The investigational medicinal product for this study is 6-mg faricimab PFS.

Patients will receive a single IVT injection of 0.05 mL of the 120-mg/mL faricimab (6-mg dose) formulation delivered via PFS with a co-packaged injection filter needle.

DURATION OF PARTICIPATION

[figure not shown]
The total duration of study participation for each patient is expected to be approximately 7 days.

INDEPENDENT DATA MONITORING COMMITTEE

An independent Data Monitoring Committee (iDMC) will not be used.

1.2 STUDY SCHEMA

Figure 1 Study Schema

BCVA=best-corrected visual acuity; FPI=first patient in; HCP=health care provider; ICF=Informed Consent Form; IFU=Instructions for Use.

Note: There will be approximately 2–3 HCP teams, with 35 patients in total. Study start corresponds with Day 1 (FPI). Study end is 7 days after the injection in the last patient. The injection procedure (study Day 1 in the schematic) can occur on different calendar days for different HCPs and different patients. HCPs will review the IFU on their own before Day 1 of the study. HCP interviews will be conducted on Day 1.

*Baseline examinations consist of BCVA, slitlamp, and indirect ophthalmoscopy.

1.3 SCHEDULE OF ACTIVITIES

Table 1 Schedule of Activities for Health Care Providers

Health Care Providers				
	Screening	Preparation of Injection Observation	Injection Observation Period	Post-Procedure Interview ^a
Day(s)	-30 to 1	_3 to 1	1	1
Eligibility criteria	x			
IFU review phase		x		
HCP informed consent ^b		x		
Injection procedure and observation of HCP activities			x	
Post-procedure discussion ^a				x

HCP=health care provider; IFU=Instructions for Use.

^a After each patient procedure, HCPs will be reminded of the complaints procedure (see Appendix 5) to be followed in case any device failures or malfunctions were noted. Further discussion topics may be addressed, if deemed necessary by the human factors observers.

^b Pre-brief by human factors observers, with HCP informed consent signing (on the morning of Day 1 or afternoon of Day –1).

Patients				
	Screening ^a	Injection Procedure ^a	Safety Telephone Call	Safety Telephone Call
Day(s)	-30 to 1	1	3 (±1)	7 (±1)
Patient informed consent	x			
Review of inclusion and exclusion criteria	x	×		
Demographics	x			
Medical History	x			
Pregnancy test (urine)	x	x		
Baseline examination (BCVA ^b , slitlamp exam, indirect ophthalmoscopy)		x		
Injection administration		x		
Study eye predose IOP		x		
Study eye postdose IOP		x		
Finger-counting test °		x		
Adverse events		x	x	x
Concomitant medications	x	x	x	x

Table 2 Schedule of Activities for Patients

BCVA=best-corrected visual acuity; ETDRS=Early Treatment Diabetic Retinopathy Study; IOP=intraocular pressure; VA=visual acuity.

- ^a If screening and injection occur on the same day, assessments listed for both visits should be conducted only once before injection.
- ^b BCVA may be measured on any standard VA chart according to local clinical practice. Acceptable charts include ETDRS, Snellen and LogMAR. Refer to Appendix 8 for further details.

Note: in the event that a patient requires an unscheduled safety visit, the same method of VA assessment should be used as the baseline assessment.

^c Finger counting test will be performed in the study eye within 15 minutes of treatment.

2. INTRODUCTION

2.1 STUDY RATIONALE

The purpose of the clinical in-use study is to collect observations on the use of the 6-mg faricimab prefiled syringe (PFS) configuration to administer an intravitreal (IVT) injection to patients with either diabetic macular edema (DME) or neovascular age-related macular degeneration (nAMD) in an actual clinical use environment. Observations will be collected during the preparation and administration of a 6-mg faricimab IVT injection using the PFS configuration in accordance with the Instructions for Use (IFU) in the intended use environment.

The PFS configuration consists of the faricimab 6-mg PFS together with the co-packed injection filter needle (IFN).

2.2 BACKGROUND

nAMD is a form of advanced AMD that causes rapid and severe visual loss and remains a leading cause of visual impairment in the elderly (Bourne et al. 2013; Wong et al. 2014). Treatment goals are to regain and maintain vision. A key challenge with currently available anti–vascular endothelial growth factor (VEGF) treatments is the requirement for frequent and long-term administration to maintain vision gains (Heier et al. 2012; the Comparison of Age-Related Macular Degeneration Treatment Trials [CATT] Research Group 2016). There remains an unmet need for more efficacious and durable treatment.

DME, a complication of diabetic retinopathy (DR), can develop at any stage of the underlying disease of retinal microvasculature (Fong et al. 2004) and is a major cause of vision loss in working-age individuals. Despite advances with the anti-VEGF approach in DME, a significant percentage of patients do not achieve normal vision or have adequate vision required to obtain a driver's license, suggesting that anti-VEGF treatment alone does not address all the pathways underlying DME pathology.

Faricimab is an intravitreously administered, humanized bispecific immunoglobulin G1 (IgG1) antibody that selectively binds to angiopoietin-2 (Ang-2) and VEGF-A. Vitreous concentrations of both Ang-2 and VEGF-A are upregulated in patients with diabetic eye disease, and to a lesser extent, in patients with nAMD. Therefore, selective neutralization of both Ang-2 and VEGF may better stabilize pathological ocular vasculature in addition to further reducing leakage compared with anti-VEGF monotherapy. This may result in further improvement of retinal function and durability of response for patients with DME, DR, and nAMD. As of May 2022, the vial product configuration of faricimab (under the tradename Vabysmo[™]) has been approved in the United States, United Kingdom, Canada, Japan, Thailand, Switzerland, and the United Arab Emirates for the treatment of nAMD and DME by injection into the eye.

The 6-mg faricimab PFS will contain the same formulation and concentration of the drug as supplied in the faricimab vial that has been used during Phase III clinical development. The vial will be replaced by a siliconized 0.5-mL glass syringe with extended finger flange and coupled plunger rod, with a rubber tip cap closures. The outside surface of the syringe will be sterilized. There is no change in the faricimab solution composition. The 30 G \times 1/2-inch injection filter needle with extra thin wall is copackaged- with the PFS. The configuration would provide an alternative to a vial kit and is anticipated to provide a more convenient system for IVT injection.

Detailed information on faricimab is provided in the Faricimab Investigator's Brochure and information about device use in the Instructions for Use.

2.3 BENEFIT–RISK ASSESSMENT

Data from the Phase I (BP28936), Phase II (BP29647 [AVENUE], CR39521 [STAIRWAY], and (BP30099 [BOULEVARD]), and Phase III (GR40349 [YOSEMITE], GR40398 [RHINE], GR40306 [TENAYA], and GR40844 [LUCERNE]) studies provide evidence of efficacy, safety, and tolerability for the use of 6-mg IVT injections of faricimab for patients with nAMD and DME. The safety and efficacy of the 6-mg faricimab PFS configuration is expected to be the same as that for the vial configuration, which has been used during clinical development, as the administration route and technique will remain unchanged.

Refer to Appendix 3 for information on anticipated risks for faricimab and risk mitigation measures, including guidelines for managing adverse events associated with faricimab.

More detailed information about the known and expected benefits and risks and reasonably expected adverse events of faricimab may be found in the Investigator's Brochure. An assessment was conducted to determine whether there is any impact of the coronavirus disease 2019 (COVID-19) pandemic on the benefit–risk assessment of this study protocol, including, but not limited to, the patient population under study and study treatment being evaluated. Based on that assessment, no impact is anticipated and the existing safety monitoring, management guidelines, and risk-mitigation measures provided in the study protocol are considered adequate.

Taking into account the efficacy data in patients with nAMD and DME, the safety profile of faricimab and that the safety and efficacy of 6-mg faricimab PFS configuration is expected to be the same as that for the vial configuration, the benefit–risk ratio is expected to be acceptable.

3. OBJECTIVES AND ENDPOINTS

The primary objective of this study is to collect observations on healthcare providers (HCPs) using a PFS configuration in an actual clinical use environment to prepare and

administer a 6-mg faricimab intravitreal injection to patients with either DME or nAMD and as instructed in the IFU.

No patient-related efficacy or safety endpoints are planned for this study. However, in accordance with Good Clinical Practices (GCPs), adverse events (AEs), adverse events of special interest (AESIs), and serious adverse events (SAEs) occurring during the 7-day study reporting period will be summarized.

4. STUDY DESIGN

4.1 OVERALL DESIGN

4.1.1 Description of Study

The 6-mg faricimab PFS clinical in-use study is a Phase IIIb, single-arm, open-label, multicenter study in patients with nAMD or DME designed to assess the ability of the intended users, HCPs, to follow the IFU to perform an IVT injection using the 6-mg faricimab PFS configuration per the intended use. The study will collect observations related to the use of the PFS configuration.

The study will be conducted in ophthalmology clinical settings. The focus of the usability observation will be on the HCP teams. The HCP team will consist of a retina specialist and any assistants who participate in any stage of the PFS preparation and administration procedure. Approximately three HCP teams will participate in this study to administer a single IVT injection of 6-mg faricimab PFS (120-mg/mL drug concentration) using the PFS configuration for a total of approximately 35 participants.

All patients will be required to have a current diagnosis of nAMD or DME with at least one eye eligible for 6-mg faricimab IVT injection, at the discretion of the retina specialist. Both previously treated and treatment-naive patients will be eligible for enrollment. Only one eye will be selected as the study eye. If both eyes are eligible, the investigator will determine which eye will be selected for study treatment (study eye).

The same retina specialist may act as the Principal Investigator and the HCP using the PFS configuration to administer faricimab. Alternatively, a sub-investigator may perform the duties of the HCP.

4.1.2 Overview of Study Design and Procedure

A study schema is provided in Section 1.2 (see Figure 1). The schedules of activities are provided in Section 1.3 (see Table 1 and Table 2).

The study will be set up to enable usability (human factors [HF]) observations related to the use of the PFS configuration. This will be performed by the two HF observers who will be present at the study sites to observe each injection procedure. In the 30 days prior to (or including) Day 1, patients will be screened for their eligibility to participate in the trial.

As part of the information package sent in preparation for the study, each clinical study site will be provided with the IFU. Approximately 3 days prior to Day 1, HCPs will be expected to familiarize themselves with the documentation in advance and will be asked to confirm that they have read the IFU by signing an acknowledgement on Day 1. The HF observer and the additional observer will not provide a demonstration or training to HCP participants.

The HF observers will pre-brief the HCPs prior to the HF observations. When the patient is ready, the HF observers will be introduced to the patient in the administration room. The HF observers will be positioned such that they can clearly observe the entire preparation and administration process. The HCP team (i.e., retina specialist alone or retina specialist with assistant/technician, as per local procedure) will be asked to open the folding box only when the HF observers are present and to perform all preparation and administration steps in view of the HF observers. The PFS configuration should be prepared for use immediately prior to the injection, as described in the IFU. The HF observers will remain at a distance specified by the HCPs or facility and will not interrupt or interfere with the procedure. The HF observers will document HCP's performance using an assessment checklist and all administration procedures will be recorded on video to facilitate subsequent HF analysis of observations.

HF observers will ask for good visibility of all activities. To enable assessment of dose setting accuracy, HCPs will be asked to pause briefly during every procedure in order to turn and show the set dose to the observers for a closer look and brief video recording.

Should the HF observers see any HCP actions of potential safety concerns related to safe PFS use, they will not intervene, as it is considered the responsibility of the HCPs to ensure patient safety based on clinical judgement. However, participating HCPs are expected to remain aware of any potential safety concerns (should they arise due to PFS use) and take preventative actions.

Following the completion of each IVT injection, the HF observers will conduct a follow-up interview with the HCPs to discuss observations. No questions will be asked in the presence of patients or other site staff. Interview questions will focus on identifying reasons for observed actions. HCPs will be reminded of the complaints procedure for reporting observations of device failures or malfunctions (Appendix 5).

See Table 1 and Table 2 for the schedules of activities performed by the HCP during the study.

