4.2.2 Rationale for Human Factors Observations

The purpose of the usability observations is to observe the use of the PFS configuration in an actual clinical use environment to assess if there are any safety concerns remaining related to the future commercial use of the device components. At the time of the study, the PFS configuration (i.e., its device components) will have gone through full technical development, including design validation to ensure the safety of the PFS and the IFN. However, the PFS configuration will not have received market approval at this time.

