6.4 STUDY TREATMENT COMPLIANCE

When patients are dosed at the site, they will receive study treatment directly from the Investigator or designee, under medical supervision. The date and time of dose administration in the clinic will be recorded in the source documents and on the eCRF. The dose of study treatment and study patient identification will be confirmed at the time of dosing by a member of the study site staff other than the person administering the study treatment.

Details on treatment administration (e.g., dose and timing) should be noted in the source documents and on the Study Drug Administration eCRF. Cases of accidental overdose or medication error, along with any associated adverse events, should be reported as described in Appendix 2.

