Accidental overdose and medication error (hereafter collectively referred to as "special situations") are defined as follows:

- Accidental overdose: accidental administration of a drug in a quantity that is higher than the assigned dose
- Medication error: accidental deviation in the administration of a drug

In some cases, a medication error may be intercepted prior to administration of the drug.

Note: Special situations are not in themselves adverse events, but may result in adverse events.

Each adverse event associated with a special situation should be recorded separately on the Adverse Event eCRF. If the associated adverse event fulfills seriousness criteria

6-mg Faricimab Prefilled Syringe—F. Hoffmann-La Roche Ltd 55/Protocol GR43742, Version 1

or qualifies as an adverse event of special interest, the event should be reported to the Sponsor immediately (i.e., no more than 24 hours after the investigator becomes aware of the event; see Section A2-5). For 6-mg faricimab PFS, adverse events associated with special situations should be recorded as described below for each situation:

- Accidental overdose: Enter the adverse event term. Check the "Accidental overdose" and "Medication error" boxes.
- Medication error that does not qualify as an overdose: Enter the adverse event term. Check the "Medication error" box.
- Medication error that qualifies as an overdose: Enter the adverse event term. Check the "Accidental overdose" and "Medication error" boxes.
- As an example, an accidental overdose that resulted in a headache would require two entries on the Adverse Event eCRF, one entry to report the accidental overdose and one entry to report the headache. The "Accidental overdose" and "Medication error" boxes would need to be checked for both entries.

All special situations associated with 6-mg faricimab PFS, regardless of whether they result in an adverse event, should be recorded on the Adverse Event eCRF as described below:

- Accidental overdose: Enter the drug name and "accidental overdose" as the event term. Check the "Accidental overdose" and "Medication error" boxes.
- Medication error that does not qualify as an overdose: Enter the name of the drug administered and a description of the error (e.g., wrong dose administered, wrong dosing schedule, incorrect route of administration, wrong drug, expired drug administered) as the event term. Check the "Medication error" box.

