- Medication error that qualifies as an overdose: Enter the drug name and "accidental overdose" as the event term. Check the "Accidental overdose" and "Medication error" boxes. Enter a description of the error in the additional case details.
- Intercepted medication error: Enter the drug name and "intercepted medication error" as the event term. Check the "Medication error" box. Enter a description of the error in the additional case details.

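### Does the second-person dose confirmation in Section 6.4 mask dose-setting errors that the observers in Section 4.1.2 are meant to see?

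*Protocol*

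**What the plan says.** Section 4.1.2 sets up the close-up reading: "To enable assessment of dose setting accuracy, HCPs will be asked to pause briefly during every procedure", turning so that the observers can inspect and briefly film the set dose. It also describes who performs the procedure: "The HCP team (i.e., retina specialist alone or retina specialist with assistant/technician, as per local procedure". On the observers' position it says: "The HF observers will remain at a distance specified by the HCPs or facility". The same section requires the box to be opened only when they are present and every step to be done in their view. They complete a checklist, and every administration is filmed. An interview about the reasons for what was seen follows each injection. Section 8 adds that observations are audio-recorded as well as video-recorded.

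Section 6.4, on treatment compliance, requires the dose and the patient's identification to be "confirmed at the time of dosing by a member of the study site staff other than the person administering the study treatment".

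Section 4.1.1 counts as part of the HCP team "any assistants who participate in any stage of the PFS preparation and administration procedure". Section 5.1.1 brings every additional HCP involved in preparation or injection into the observations, the interviews and the HCP consent.

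Appendix 2, Section A2-7.11, recognises that "In some cases, a medication error may be intercepted prior to administration of the drug" and gives a recording rule for that case ("Intercepted medication error: Enter the drug name and" a set event term).

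Section 4.2.2 gives the purpose of the observations: "to assess if there are any safety concerns remaining related to the future commercial use of the device components".

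**The concern.** Dose setting accuracy is the one performance measure that Section 4.1.2 names, and the protocol adds a pause to every procedure to read it. A confirmation by a second person also falls around dosing, and neither section mentions the other. If the confirmation comes first, the close-up shows the result of user plus checker. If the showing comes first, it shows the user alone. If sites differ, the readings mix the two. The study is meant to assess whether intended users can follow the instructions and whether safety concerns remain for commercial use, so it matters which of these is read. Section 6.7 links excess injection volume to raised intraocular pressure, so a hidden setting error would be relevant to safety.

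Two further points seem to follow. A specialist working alone, which Section 4.1.2 allows, seems unable to meet a rule that needs a second person. And nothing in Section 4.1.2 sends a setting corrected at the check or the pause to the intercepted-error rule in A2-7.11.

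**Working it through.** **The plan's own figure.** Section 9.2 gives about 12 patients per team and at least three teams: 12 × 3 = 36, consistent with the stated 35 or so (minimum 30). No figure in the protocol is disputed.

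**How large the effect on the close-up could be.** Let p be the chance that a setting is wrong, c the chance that the check corrects it before the showing, and N the number of procedures, taken as independent. The protocol gives neither p nor c; both are assumptions.

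- Showing first: P(at least one wrong setting shown) = 1 − (1 − p)^N.
- Confirmation first: P = 1 − (1 − p(1 − c))^N.

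| N | p | Showing first | Check first, c = 50% | Check first, c = 90% |
|---|---|---|---|---|
| 35 | 2% | 51% | 30% | 7% |
| 35 | 5% | 83% | 59% | 16% |
| 35 | 10% | 97% | 83% | 30% |
| 30 | 5% | 79% | 53% | 14% |

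For N = 35 and p = 5%: 1 − 0.95^35 = 0.834; 1 − 0.975^35 = 0.588; 1 − 0.995^35 = 0.161. The expected numbers of wrong settings shown are 35 × 0.05 = 1.75, then 0.875, then 0.175. With c = 0 the order makes no difference.

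**What the formula leaves out.** It treats an error corrected before the pause as lost. Let d be the chance that such a correction is captured by the observers, the recordings or the interview. The probability of learning of at least one error is then 1 − (1 − p(1 − c(1 − d)))^N. For N = 35, p = 5%, c = 90%:

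- d = 0: 16%, as above.
- d = 50% (an assumed midpoint): p(1 − c(1 − d)) = 0.05 × 0.55 = 0.0275, and 1 − 0.9725^35 = 62%.
- d = 1: 83%, the same as showing first.

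The loss therefore depends on d, and Sections 4.1.2 and 8 are written to make d high.

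**Does Section 6.4 check the setting at all?** It pairs the dose with patient identification in a compliance section, which reads like a check of right treatment and right patient. For the plunger, Section 4.1.2 uses different terms (dose setting, set dose), and Section 6.4 uses neither. If only the labelled product is confirmed, then c = 0 and the order is irrelevant.

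**Specialist alone.** Section 6.4 asks for a member of the site staff, not a member of the HCP team, and Section 4.1.2 itself separates HCPs from other site staff when it sets the interview rule. One person can prepare and inject while another confirms. If the confirming person is an HCP involved in the preparation or injection, Section 5.1.1 already includes that person in the observations, interviews and consent. The passages can all be followed together.

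**Intercepted errors.** A2-7.11 applies to all special situations with the study product, whether or not an adverse event results, and names intercepted errors. Sections 6.1 and 6.4 already point to Appendix 2.

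**The case for a change.** The strongest argument for a change is that the narrow reading of Section 6.4 is not certain. The study has one product, one strength and one dose, and Section 6.5 allows no modification. What can vary at the moment of dosing is the volume set: 0.05 mL from a 0.5 mL syringe. On that view the second person would naturally look at the plunger. The close-up was added because a view from a distance was not thought enough to judge the setting, so general video may show that a correction happened without showing how wrong the setting was. The protocol gives no rule for scoring a prompted correction, and a clarifying sentence would cost almost nothing.

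Part of this stands. The order is not stated, the meaning of dose in Section 6.4 is open, and under the wider reading the close-up could show a corrected setting. What does not stand is that the error would be hidden. The observers see the whole sequence, a spoken prompt is on the audio, and the interview asks why actions were taken. The magnitude of an error corrected before the pause might be lost; the fact of the correction probably would not be. The proposed remedy also asks only that some order be stated, not a particular one, so it would not by itself ensure that the reading describes the user alone.

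**Conclusion.** No change to the plan is needed. This is missing procedural detail, not a contradiction or a faulty measure. The drop from 83% to 16% holds only if three assumptions hold together: the Section 6.4 check covers the set volume, it comes before the showing at every site, and nothing but the close-up captures a correction. The first is unsettled in the text, the second is not stated, and the third conflicts with Sections 4.1.2 and 8. The probabilities also assume independent procedures, although about three teams perform about 12 each.

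Sections 3 and 9.1 make this a study that collects observations and tests no hypothesis, and no error rate or detection probability is a target. An analyst who finds a setting changed before the pause can report it as a corrected use error from the checklist, recordings and interview. The order of steps and the scoring of corrections would naturally sit in the observers' checklist, pre-brief or observation forms, which are not part of the protocol and were not available. The specialist-alone option and the intercepted-error rule work as written.
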